## 1.0 PURPOSE

### **1.1 Name and Intended Use**

The device used in this study is called the Brera/Med 400 device.

The intended use of the Brera/Med 400 device in this study to assess the safety and efficacy of the adhesive electrodes for muscle stimulation and the treatment of abdominal fat on the abdomen and/or flanks.

### **1.2 Objectives**

1. Primary Objective:
  - Evaluation of adverse events and side effects throughout the study.
2. Optional Assessments:
  - Photographic evaluation with correct identification of pre-treatment 2D images when compared to the 30 and 90 day follow up images performed by three independent reviewers.
  - Abdominal circumference reduction evaluated using a tape measurement.
  - Principle Investigator assessment using the Global Aesthetic Improvement Scale Abdominal fat reduction evaluated using an ultrasound device
  - Principle Investigator assessment using the Global Aesthetic Improvement Scale (PGAIS) at the 30 and 90 day follow up visit.
  - Subject Questionnaire(s)
    - The Global Aesthetic Improvement Scale (SGAIS) at the 30 and 90 day follow up visit.
    - Subject satisfaction at the 30 and 90 day follow up visit.
    - Psychometric Questionnaire (muscle firmness, hardness, self-image, and well-being)
    - Subject Treatment Questionnaire
  - Collection of 3D Photography
  - Objective measurement of abdominal muscle strength.
  - Temperature monitoring.
3. Additional Safety Objectives:
  - Collection of Treatment Discomfort/Pain Evaluation

### **1.3 Duration of the Investigation**

The sponsor anticipates that all subjects can be enrolled within 6 months. If subject participates in all required visits, then the subject's participation in this study may last up to 5 months. It is anticipated that it will take approximately 3 months to analyze the data collected during this study. The total duration of this study is anticipated to last approximately 14 months.

## 2.0 PROTOCOL

### **2.1 Protocol Methodology and Analysis**

Methodology:

Subjects are to be enrolled in this clinical study if they are a healthy male or female 18 years of age or older. Up to 30 subjects will be enrolled at 1 study center. Subjects will be enrolled into 2

groups, Group A and Group B. Subjects will be enrolled in Group A if they present with abdominal fat and are able to be present for all visits as outlined in “Schedule of Visits and Procedures – Group A”. Subjects will enroll in Group B for training and experience purposes only and will follow the visit schedule as outlined in “Schedule of Visits and Procedures – Group B”. Randomization will not be required as each subject will be assigned to a group depending on the purpose of their treatment(s). All subjects will attend a screening/pretreatment visit which may be performed on the same day as the treatment visit.

Subjects in Group A will receive up to 8 treatments with the Brera/Med 400 device on their abdomen or flanks. Subjects may receive a phone call 1 week (1-7 days) after each treatment to record side effects. Subjects will return for follow up visits at 30 and 90 days post last treatment for efficacy and side effects assessments.

Subjects in Group B may receive up to 8 treatments with the Brera/Med 400 device on their abdomen and/or flanks. Subjects may receive a phone call 1 week (1-7 days) after each treatment to record side effects. Subjects may be asked return for follow up visits at 30 and 90 days post last treatment for efficacy and side effects assessments.

An unscheduled visit or phone call may be performed at any time during the study at the request of the subject or as deemed necessary by the site Investigator.

#### Analysis:

Upcoming generations are proving to have an interest in non-ablative aesthetic treatments and will drive demand for innovated products, procedures, and practice design.i Due to this shift in patient base, practices need to evolve to adapt to the newer generational ideologies. There have been rapid advances in RF technology over the past few years and the nonsurgical treatment using this energy source offers great promise to our aging population.ii Radiofrequency technology used for muscle stimulation and fat reduction needs to be further investigated to optimize treatment parameters for safe and effective non-ablative aesthetic treatments.

#### Relevance:

Non-invasive fat reduction is a commonly sought out procedure and continues to increase in demand (+3% from 2018 to 2019)iii perhaps due to the fact that, according to the CDC, the prevalence of obesity in the U.S. was 42.4% in 2017-2018.iv Currently, the treatments available for non-invasive muscle building and fat reduction include, but not limited to, radiofrequency, HIFEM, and bio-electric current stimulation. The limitations of current products on the market include different side effect profiles and modes of administration.

#### Testability:

Emsculpt Neo® is intended for non-invasive lipolysis (breakdown of fat) of the abdomen and thighs and reduction in circumference of the abdomen and thighs with Skin Type I to Skin Type VI. Emsculpt Neo® is also cleared for improvement of abdominal tone, strengthening of the abdominal muscles and development of firmer abdomen. Strengthening, toning, firming of buttocks, thighs, and calves. Improvement of muscle tone and firmness, for strengthening muscles in arms. TruSculpt device has been cleared for used for reduction in circumference of the abdomen and non-invasive lipolysis (breakdown of fat) of the abdomen (K180709). These devices

performed studies which utilized the following evaluation methods: circumferential measurements, histology, subject assessment of improvement and satisfaction.. This particular study will utilize the collection of before and after photography for blinded, independent review of clinical photographs, ultrasound and circumferential measurements, 3D quantification of volume reduction, satisfaction scores, and safety data to evaluate the safety and efficacy of the treatment.

#### Compatibility:

Due to such a high prevalence of obesity in the U.S. and the increasing demand for non-invasive muscle toning and lipolysis treatments, there is a need to treat unwanted fat in its earlier stages to optimize treatment outcomes. As a subject gets older or the condition worsens, their treatment may need to be more aggressive to get their body to respond the same way that a younger subject or less severe case may be able to respond.

#### Predictive power:

While this study will observe the effects of the device on muscle stimulation and fat reduction on the abdomen and flanks, results could potentially be applied to a variety of body areas and other potential applications. Assuming that there is significant improvement, it would be appropriate to expect results in different areas where other products and devices have significant results.

### **2.2 Protocol Study Design**

This is a prospective, open label, single center clinical study to collect safety and efficacy data on the Brera/Med 400 device.

### **2.3 Subject Selection Criteria**

Subjects will meet the criteria described below:

#### Inclusion Criteria:

- A healthy male or female 18 years of age or older.
- Agrees to be treated with the Brera/Med 400 device.
- Understands and accepts obligation not to receive any other procedures on the treatment area through the length of the study.
- Understands and accepts the obligation and is logistically able to be present for all visits.
- Is willing to comply with all requirements of the study and sign the informed consent document.

#### Exclusion Criteria:

- Is pregnant or of childbearing potential and not using medically effective birth control, or has been pregnant in the last 3 months, currently breast feeding or planning a pregnancy during the study.
- Is currently enrolled in an investigational drug or device trial, or has received an investigational drug or been treated with an investigational device within in the area to be treated 6 months (or at the discretion of the Investigator) prior to entering this study.
- Has injured (such as a cut, wound) or infected skin, or has presence of evident pathologies such as melanomas or other tumors of the skin, dermatitis, eczema, psoriasis, etc. in the area to be treated.
- Is on local, oral, or systemic anesthetic agents.

- Has nerve insensitivity to heat in the treatment area.
- Has received an organ transplant.
- Has any embedded electronic device that gives or receives a signal, the device should be turned off or removed prior to treatment.
- Has an embedded pacemaker or implantable cardioverter defibrillator (ICD), the client's cardiologist must be consulted prior to treatment.  
**NOTE:** This device has not been tested on patients implanted with electronic devices that receive or emit signals, such as: Pacemakers, Implantable Cardiac Defibrillators (ICD), or Cardiac Resynchronization Therapy (CRT) devices.
- If the neutral pad would need to be placed on a subject that has a metal plate, rod, or any metal implant that could conduct heat.
- Has an allergy to adhesives, such as glues on medical tape, they should be alerted that a rash may occur on the applicator and neutral pad site, and an over-the-counter solution may be used to treat the area.
- Has an unhealthy expectation of the results – this is not plastic surgery and all subjects should be fully informed of the treatment's expected results.
- Has severe laxity or sagging that causes redundant folds of tissue or hanging skin in the area to be treated – this treatment will be ineffective.
- Has used Accutane (Isotretinoin) six to twelve months prior to treatment, as this can thin the skin and make it brittle.
- Is currently taking anticoagulants.
- The treatment area has scars and/or tattoos.
- Has any of the following conditions:
  - Thrombosis or Thrombophlebitis
  - Active Vascular Disease
  - Labyrinthitis and Tinnitus
  - Liver Disease or Dyslipidemias
  - Acute Sepsis
- Has any condition or is in a situation which in the investigators opinion may put the subject at significant risk, may confound study results or may interfere significantly with the subject's participation.

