**Cautionary Criteria:**

- Has any of the following conditions:
  - Autoimmune Disease
  - Diabetic
  - Herpes Simplex

Be sure to list all concomitant medications taken or procedures performed before, during and after the trial

Subjects will be recruited for the study through the existing patient database and may also be recruited through advertisements.

Subject populations will not be eligible to participate in the study if they are vulnerable populations such as children, pregnant women, prisoners, institutionalized individuals, and any persons requiring a legally authorized representative as part of the consenting process.

Subject population characteristics that will not be eligible to participate in the study include non-English speaking individuals and people who cannot read or comprehend English. Employees of the Investigator will be participating in the study.

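### The two implanted-electronics exclusions end in pre-treatment steps, so the text leaves open treating a subject whose implant is switched off or whose cardiologist has been consulted

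*Combined protocol and SAP*

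**What the plan says.** Two items under Exclusion Criteria in section 2.3 concern implanted electronics:

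- General item: "Has any embedded electronic device that gives or receives a signal, the device should be turned off or removed prior to treatment".
- Cardiac item: "Has an embedded pacemaker or implantable cardioverter defibrillator (ICD), the client's cardiologist must be consulted prior to treatment".

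A NOTE attached to the cardiac item states: "This device has not been tested on patients implanted with electronic devices that receive or emit signals". It gives examples: "such as: Pacemakers, Implantable Cardiac Defibrillators (ICD), or Cardiac Resynchronization Therapy (CRT) devices".

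A separate list in the same section, headed "Cautionary Criteria", names autoimmune disease, diabetes and herpes simplex. Implants are not on it. Sections 2.4 to 2.7 (screening, consent, pre-treatment and treatment procedures) do not mention implants.

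**The concern.** An exclusion criterion normally ends once the condition is stated, because nothing further happens to an excluded person in the study. These two items go on to say what to do before treatment. A coordinator could take them as conditional: excluded unless the implant is off, or unless the cardiologist has been contacted.

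On that reading, a subject with a pacemaker, ICD or CRT device could be treated, or could have the implant switched off in order to be treated. Section 3.2 calls the procedure elective. Section 3.3 describes the study device as uncleared and with little safety data so far, and section 4.0 gives radiofrequency power of up to 400 W. The protocol names nobody to switch an implant off, watch the subject meanwhile or restore its function. The cardiologist is to be consulted, but nothing says that the cardiologist must agree.

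**Working it through.** No arithmetic applies and the plan states no figure to reproduce. The check sets the wording of the list side by side and then looks for text elsewhere that would settle the reading.

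**1. What follows the condition in each kind of item (section 2.3)**

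| Item | Text after the condition | Does it presuppose treatment? |
|---|---|---|
| Organ transplant; anticoagulants | None | No |
| Metal implant: "a metal plate, rod, or any metal implant that could conduct heat" | None; the item depends on where the neutral pad would go, but gives no handling step | No |
| Severe laxity | A reason: "this treatment will be ineffective" | No |
| Isotretinoin | A reason: "as this can thin the skin and make it brittle" | No |
| Any signal-handling implant | Turn off or remove before treatment | Turn off: yes. Remove: no |
| Pacemaker or ICD | Consult the cardiologist before treatment | Yes, in the main |
| Adhesive allergy | Warn of a possible rash, which may be managed with an over-the-counter product | Yes |

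The reasons given for laxity and isotretinoin explain an exclusion. The two implant clauses are instructions, and they do not explain one.

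**2. Separating the two branches of the general item.** If the implant has been removed, the subject no longer carries one and the NOTE no longer applies. That branch is of no concern. The switched-off branch is different, because the subject still has the implant. The NOTE speaks of patients who are implanted and makes no exception for an implant that is off.

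**3. Does the heading settle it?** Not on its own. The adhesive-allergy item sits under the same heading, yet it is written as a precaution for someone who will be treated. The list therefore mixes exclusions with precautions. That item is a separate, minor clarification.

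**4. Does another section settle it?**

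- Section 2.3, inclusion: the subject must be healthy; implants are not mentioned.
- Section 2.3, last exclusion: the investigator may exclude anyone judged to be at material risk. This is discretionary.
- Section 2.4: the criteria are verified at screening.
- Section 2.5: subject numbers go only to people who satisfy every criterion and have consented.
- Sections 3.1 to 3.3, 4.0 and 5.0: no statement that people with implants may never be treated.

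Sections 2.4 and 2.5 apply the criteria but do not interpret them. If the criterion is read as conditional, a subject with a switched-off implant passes both checks.

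**Result.** Neither the list nor the later sections rule out the conditional reading.

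**The case against.** The strongest reply is that an ordinary reader would already exclude these people. Each item states a complete excluding condition under an exclusion heading. Cautions have their own list, and implants are not on it. The NOTE reads naturally as the reason for exclusion. Eligibility is checked before a subject number is assigned, and the investigator-opinion item is an independent route to exclusion that the NOTE would prompt. Device and protocol training (section 3.3), sponsor training and monitoring (section 5.0) and labeling of contraindications (section 6.0) lower the risk further. The Operator Manual, Clinical Reference Guide and consent form are attachments that could not be checked, and they may contain a firm contraindication.

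Most of this stands. It makes exclusion the likelier intent and lowers the chance of harm. It does not explain why the two clauses are there.

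Three stronger inferences are tempting, and the documents do not support them:

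- *That the protocol admits people with implanted cardiac devices.* No section says so, and the structure points the other way. The text only fails to close that reading.
- *That CRT devices fall between the two items because only the NOTE names them.* The general item covers any signal-handling implant, and the NOTE counts CRT devices among these, so they are covered.
- *That same-day screening and treatment, allowed in section 2.1, shows that such subjects would be treated.* That rule is compatible with either reading.

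**Conclusion.** The point holds as a wording defect with a subject-safety consequence. Two items listed as exclusions carry instructions that belong to subjects who will be treated, next to a statement that the study device is untested in people with such implants. The wording should be corrected.

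Its size cannot be given as a number. The documents do not say how many candidates carry implants or what the risk per treatment would be. Section 2.1 caps enrollment at 30 subjects at one center, so few could be exposed. The likelihood appears low and the possible harm to an individual serious.

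The conclusion rests on the protocol text alone. It assumes that the eligibility form and the unseen attachments do not already state an absolute bar. If they do, the practical risk is smaller, but the protocol should still agree with them. The planned statistical analysis is not affected.

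**What to change.** In section 2.3, replace the two items with one unconditional exclusion, for example: *Currently has an implanted electronic device that sends or picks up signals, including a pacemaker, ICD or CRT device, whether switched on or off.*

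Delete the turn-off-or-remove clause and the cardiologist clause. The word *currently* keeps a person whose implant has already been taken out for other reasons eligible. Retain the NOTE as the rationale, and bring the eligibility case report form and consent form into line.

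The cost is a wording amendment with written IRB approval, as section 21.0 requires, and possibly a few fewer eligible subjects. If exclusion was always intended, no eligible subject is lost. No visits or procedures are added.

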#### **2.5 Informed Consent Process and Enrollment**

Subjects will be asked to review the pre and post treatment instructions prior to signing the informed consent form and their involvement in the study. Subjects will be informed of site's COVID-19 procedures that adhere to federal and state guidelines at this time. Subjects who sign the informed consent will be screened to confirm eligibility and, if eligible, will be assigned a subject identification number. Subjects will be de-identified through their subject identification number, which will be stored in a secure location. Subject identification numbers will be generated chronologically and assigned only to subjects who have met all the study selection criteria and have signed the informed consent form. The informed consent will be obtained prior to a subject's involvement in any study related procedures. A subject will be considered enrolled in the study once they have signed the informed consent form.

The following Pre-Treatment instructions will be reviewed:

- Shave any visible hair on the area to be treated.
- Do not wear constrictive clothing. Your abdomen or flanks must be accessible for the neutral pad to be attached.
- Remove all makeup and lotions from the treatment area and all jewelry and metal objects from the body.
- For an optimum treatment, keep hydrated by drinking water (at least 8 cups daily) or hydrating fluids, such as Gatorade, and avoid drinking alcohol for 24 hours in advance.

The following post treatment instructions will be reviewed:

- If the skin is slightly pink or red in areas following the treatment, avoid hot water when washing or showering until any erythema (redness) has subsided.
- Soothing creams or moisturizers, such as Aveeno, may be used.
- Gently massage the treated area daily for 5 minutes for the duration of your involvement in the study.
- Use a sun block with UVA and UVB protection with SPF of 30 or greater to prevent sun damage.
- Maintain the same weight and exercise routine throughout the study.

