## **2.7 Treatment Procedures**

- The defined study area will be identified and may be marked with a surgical marker.

- Procedures for the Brera/Med 400 treatment:
  - The applicators will be placed in contact with the skin.
  - The entire defined treatment area will then be treated by delivering energy to the skin.
  - Temperature may be continuously monitored and recorded during treatment.
- Parameters may be adjusted throughout the treatment to increase subject comfort.
- Subjects will be asked to report the general level of treatment discomfort/pain on a scale of 0 (none) to 10 (maximum intolerable pain).
- Photographs may be taken during treatment.
- The additional treatments will follow the same procedure.

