**Temperature Monitoring:**

An infrared thermometer may be used for temperature monitoring to measure temperature on the skin before, during, and after treatment.

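### The only exclusion naming passive metal implants depends on a neutral pad that the treatment steps in Section 2.7 do not mention

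*Combined protocol and SAP*

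**What the plan says.** Section 2.3 (Exclusion Criteria) has three bullets on implants. Two concern electronic devices: anything that gives or receives a signal, and pacemakers or defibrillators. The third is the only one that reaches passive metal. It opens "If the neutral pad would need to be placed on a subject that has a metal plate, rod, or any metal implant" and ends by limiting the concern to metal that might conduct heat.

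The pad appears twice more in the operative text. The adhesive-allergy bullet in Section 2.3 refers to a rash at the applicator and pad sites, and the pre-treatment instructions in Section 2.5 tell the subject: "Your abdomen or flanks must be accessible for the neutral pad to be attached".

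Section 2.7, which sets out how treatment is given, has no pad step. It says "The applicators will be placed in contact with the skin" and then "The entire defined treatment area will then be treated by delivering energy to the skin".

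**The concern.** An exclusion that begins with a condition works only when the condition can be met. Here the condition is placement of a pad, and the section describing the procedure does not place one. A site that follows Section 2.7 to the letter, with no pad, would find that the bullet excludes nobody. A subject with a plate, rod or other heat-conducting implant in the abdomen or flanks could then enrol without breaching any exclusion that names passive metal.

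What is at stake is subject safety. No estimate or test is affected. Section 2.14 lists skin burns among the anticipated side effects. Section 3.3 says the device is uncleared with limited safety data, and describes energy passing through the skin to fat and muscle, though it adds that the epidermis is not damaged. Section 2.1 allows up to 8 treatments per subject.

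**Working it through.** No calculation applies. The check sets the sections side by side, using the current text only and leaving the revision log in Appendix A aside.

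1. **Exclusions that name passive metal.** Section 2.3 has 17 top-level exclusion bullets. Three concern implants: 2 electronic and 1 passive metal. The passive-metal bullet is the conditional one, so no exclusion names passive metal independently of the pad.

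2. **Mentions of the neutral pad.** Section 2.3 has 2 (metal bullet, adhesive bullet), Section 2.5 has 1 and Section 2.7 has 0. That is 2 + 1 + 0 = 3 mentions, none in the treatment steps.

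3. **Case A, a pad is used.** The bullet operates. Its wording may cover any subject with such metal, wherever it lies. Section 2.5 also suggests that the pad goes on the abdomen or flanks, so even a rule confined to the pad site would reach much of the treated region. No gap is claimed. The defect is only that Section 2.7 omits the placement step.

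4. **Case B, no pad is used.** The condition is never met and the bullet removes no one.

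5. **What remains in Case B.**
   - The last exclusion lets the investigator exclude anyone judged at significant risk. It does not mention metal.
   - "The treatment area has scars and/or tattoos" would catch some subjects with surgical hardware, but only where there is a scar in the treatment area.
   - Medical history is taken at screening (Section 2.4), with no stated question about metal implants.
   - Temperature checks are optional: "Temperature may be continuously monitored and recorded during treatment". Section 2.13 says an infrared thermometer "may be used for temperature monitoring to measure temperature on the skin before, during, and after treatment", so the reading is of skin and not of tissue around deeper metal.
   - Labeling and the Operator Manual (Section 6.0 and the attachment list) may carry a contraindication. They were not available for this review.

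6. **Does the heat concern extend from the pad to the applicators?** No section says so. Three things are consistent with it: the bullet's own reference to conducting heat; the other heat-related exclusion, "Has nerve insensitivity to heat in the treatment area", which concerns the area where the applicators act; and the Section 2.5 instruction to take off jewelry and metal objects, which does not depend on a pad. That instruction gives no reason, and Section 13.0 asks for jewelry to be removed for photographs, so it is weak support. The extension remains an inference.

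**The case against.** The strongest reply is that Section 2.7 is silent on the pad and does not forbid it. It is a brief outline that also omits power and duration, and Section 6.0 refers the reader to the Operator's Manual for directions. Every operative mention of the pad presumes that one is used, so a screener working from Sections 2.3 and 2.5 would expect a pad and apply the bullet. This stands, and it is why the point is limited to the no-pad case.

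Second, if the sponsor's concern was only with metal at the pad, a bullet that falls silent when there is no pad is behaving correctly. This stands in part. The documents do not show an applicator-side hazard, but they do not show that heat-conducting metal under an applicator was considered and judged acceptable either.

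Third, other safeguards exist: the requirement that subjects be healthy, the screening history, adjustment of parameters for comfort, and the investigator's experience. They reduce the risk, but none names metal.

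Two stronger readings are tempting and should be resisted.
- A reader might infer from the entry in Appendix A about removing the pad that the exclusion is already dead. A change log does not establish what the current text requires, and the current text still refers to a pad.
- A reader might infer a drafting error because 5 of the 17 exclusions are tied to the area being treated and this one is not. But 17 − 5 = 12 are not so tied, including both electronic-implant bullets, so the count is not evidence of an error.

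**Conclusion.** The point holds in a narrow form. Sections 2.3 and 2.5 presume a neutral pad and Section 2.7 contains none. If treatment is given as Section 2.7 describes, without a pad, the single exclusion that names passive metal has no effect and protection becomes indirect.

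This rests on two assumptions: that treatment may in fact proceed without a pad, which the text leaves open, and that heat-conducting metal at the applicator site deserves the same caution as metal at the pad, which is inferred. A reader might go further and conclude that subjects with implants will be harmed or will be treated unassessed. The documents support neither conclusion: they give no implant prevalence and no burn rate, and investigator discretion remains. The point bears on the clarity of a safety criterion and changes no analysis. It is worth correcting because the correction is cheap.

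**What to change.** Reword the bullet so that it no longer depends on the pad. For example: *Has metal hardware (plate, rod or other implant) able to conduct heat within the treatment area, meaning under or adjacent to the applicators, or, if a neutral pad is used, at the pad site.*

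Then settle the pad question in one direction. If no pad is used, delete the pad wording from Section 2.3 (2 places) and Section 2.5 (1 place), and drop the pad clause from the new bullet. If a pad is used, add a placement step to Section 2.7. Bring the separate pre-treatment instructions given to subjects into line.

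The cost is a short wording amendment with the written IRB approval that Section 21.0 requires, and possibly a few additional screen failures.

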#### **2.4 Screening**

Subjects will be asked questions about their medical history, may have a limited physical and their inclusion/exclusion criteria will be verified. Discontinuation of any concomitant medications will be discussed, and pretreatment instructions and post treatment instruction will be reviewed with the subject.

Procedure for the Limited Physical Exam:

If the investigator determines that a limited exam is necessary, the exam will be like a basic annual physical exam performed by a primary care doctor to determine general overall health. The limited medical exam may include all or any of the following; vital signs such as blood pressure, heart rate, respiratory rate and body temperature, general appearance, listening to the heart, lungs and abdomen with a stethoscope, head and neck exam, in addition to examining the throat, tonsils, teeth, ears, eyes and nose as well as a neurological exam such as testing muscle strength, reflexes, balance, sensory changes of the extremities and mental state.

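### The isotretinoin exclusion in 2.3 does not fit its own reason: read literally it leaves out current and recent use, and read as a look-back it has no defined cut-off

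*Combined protocol and SAP*

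**What the plan says.** The Exclusion Criteria in section 2.3 hold the only mention of isotretinoin in the supplied text: "Has used Accutane (Isotretinoin) six to twelve months prior to treatment, as this can thin the skin and make it brittle". The line has two parts, a time window and a reason for it.

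Three other provisions bear on the point:

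- The last exclusion criterion is a general one, left to the investigator's judgement: "Has any condition or is in a situation which in the investigators opinion may put the subject at significant risk". It extends to anything that may confound the results.
- The end of 2.3, under Cautionary Criteria, asks that medications taken before, during and after the trial be listed.
- Section 2.4 has medical history taken at screening and adds: "Discontinuation of any concomitant medications will be discussed".

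None of these names isotretinoin or gives a period for it.

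**The concern.** An exclusion based on a drug's effect on the skin would be expected to apply at least as strongly to use just before treatment as to use many months earlier. This one, as worded, starts at six months and runs backwards. A screener who follows the words finds nothing in the line against a subject whose use falls wholly within the last six months.

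What is at stake is subject safety first and the reading of the results second. Adverse events are the primary objective (1.2). Section 2.14 lists burns, crusting, bruising and scarring among the possible device effects, and 3.3 acknowledges that safety data on the device are limited. The study is open label, and 2.15.6 summarises safety without any comparison. If a subject with drug-affected skin had a skin event, no planned analysis would separate the drug's contribution from the device's.

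**Working it through.** No figure in the plan needs to be reproduced and no arithmetic applies. The check is to apply the criterion under each reasonable reading, then compare it with its neighbours and with the provisions that might fill the gap.

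**Step 1: the window and the reason.** The window is "Has used Accutane (Isotretinoin) six to twelve months prior to treatment". The reason is "as this can thin the skin and make it brittle". The window is bounded at both ends, and no word carries it up to the day of treatment. The reason contains nothing that would make recent use less relevant than older use. The documents do not say how long the skin effect lasts, so the conflict is one of logic, not of a figure.

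**Step 2: apply each reading.** The criterion turns on whether the drug was used in the window, so cases are sorted by when use took place.

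| Timing of use before treatment | Literal window (twelve to six months) | Look-back of six months | Look-back of twelve months |
|---|---|---|---|
| Ongoing, begun within the last six months | not covered | excluded | excluded |
| Begun and ended within the last six months | not covered | excluded | excluded |
| Ended nine months ago | excluded | not covered | excluded |
| Ended more than twelve months ago | not covered | not covered | not covered |

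The literal reading fails in the first two rows, the cases closest to treatment. One limit applies: a long course that is still running, or ended recently, but reaches back past six months does meet the literal criterion through its earlier part. The literal gap is therefore use confined to the last six months, whether or not it continues. The two look-back readings close that gap but disagree in the third row, and the text does not choose between them.

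**Step 3: the neighbouring criteria.** The same list shows how the plan words a period that reaches the present, "has been pregnant in the last 3 months", and how it words present use of a drug, "Is currently taking anticoagulants". The isotretinoin line does neither. The criterion on previous investigational products gives a single period of six months and says outright that the investigator may vary it. The isotretinoin line gives a range and no such permission, so the range cannot safely be read as a choice left to the investigator.

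**Step 4: the provisions that might fill the gap.** The discretionary exclusion is broad enough to reach a recent user, if the investigator learns of the use and judges it a significant risk or a confounder. The medication list and the medical history may bring the use to light. The discussion of discontinuation concerns drugs being taken now; it is not an eligibility rule and does not reach a course already stopped. These provisions work case by case, and none tells the screener which period counts.

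**The case against.** The strongest answer is that nobody would read the line literally. The reason stands in the same sentence and points to a washout period written as a range. The list is loosely drafted elsewhere, so a missing word is the likely explanation. The study has one center and an investigator chosen for experience with such systems (3.2), who has both reason and authority under the discretionary criterion to turn a recent user away. One clarification to that center would settle the matter.

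Much of this stands. The gap is probably a drafting slip. A reader might infer that the plan deliberately accepts recent users, or that the site would necessarily enroll them. The documents support neither: not meeting one exclusion is not the same as being admitted, and the discretionary criterion remains.

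A reader might also infer a shift in the adverse-event percentage. One subject with an event is 1/20 = 5 percentage points with the 20 subjects in 2.15.2, or 1/30 = 3.3 points with the 30 in 2.1 and 3.3. But that is true of any subject with any event and says nothing about isotretinoin. Nor would either figure cross a limit in the plan: 2.15.1 rests success on the physician's judgement of the side-effect profile, with no numerical threshold.

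What the answer does not remove is the defect itself. The washout reading, taken at its best, still leaves the eligibility of a course that ended nine months ago undecided.

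**Conclusion.** The point holds as an inconsistency within a safety criterion. On the literal reading the exclusion omits the period nearest to treatment, against its own reason. On the look-back reading its length is undefined between six and twelve months. Neither reading yields a rule that both serves the stated purpose and can be applied the same way to every candidate.

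Its size cannot be put as a number. The documents give no rate of isotretinoin use among candidates, no duration of the skin effect and no added risk of skin events, so no effect on the event rate can be stated. Sample size, power and error rates are untouched. The conclusion rests only on the wording of 2.3 and on the absence of any other isotretinoin rule in the supplied text. The general safeguards lower the practical risk but do not correct the line. It should be amended because it concerns subject safety and is cheap to put right.

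**What to change.** The sponsor should reconcile the time window in 2.3 with its stated reason, so that the criterion gives one unambiguous period with no unintended gap before treatment. The wording should make plain how current use is classed and from which point the period is counted. The length is for the sponsor to decide, and none is proposed here. The same wording should be used in whatever documents the site uses at screening. These were not supplied, so whether they repeat the present line is unknown.

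The cost is a one-line amendment with written IRB approval under section 21.0. No visit, procedure or analysis changes.
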